#### **5.3.1. Inclusion criteria**

Patients must meet all the following inclusion criteria in order to be eligible for inclusion in the study:

- Patient has a minimum of 1-year post-operative follow-up data available, or complete data to death

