## 2. SYNOPSIS

Title:	A Retrospective, Observational, Multicentre Study to Collect Clinical Safety and Performance data on POLYMAILLE® C vascular prosthesis
Study Population:	Subjects who did receive POLYMAILLE® C at least one year ago for replacement or bypass of arteries. 2 main sub-populations will be studied depending on location of surgery (abdominal and peripheral), but data will be collected for all subjects who did receive POLYMAILLE® C.
Study Design:	Multi-center retrospective case series
Study Type:	PMCF
Number of subjects:	Data from a minimum of 200 subjects will be evaluated. A minimum of 100 subjects will be evaluated for each main location of surgery (abdominal and peripheral).
Follow-up	At least 1 year follow-up after surgery until a maximum of 5 years.
Study Product:	POLYMAILLE® C vascular prosthesis
Intended use:	POLYMAILLE® C vascular prostheses are indicated for replacement or bypass of arteries presenting aneurysm or obliterative arterial disease. Their indication is restricted to abdominal and peripheral surgery not crossing the knee flexion crease.
Objectives:	Describe safety and performance of POLYMAILLE® C
Performance primary endpoint:	Primary patency rate at 1 year after surgery using POLYMAILLE® C
Safety primary endpoint:	Mortality rate at 30 days after surgery using POLYMAILLE® C
Performance secondary endpoints:	
 
• Procedural success rate
 
• Primary patency rate at 30 days and 6 months after surgery using POLYMAILLE® C
 
• Primary assisted patency rate at 30 days, 6 months and 1 year after surgery using POLYMAILLE® C
 
• Secondary patency rate at 30 days, 6 months and 1 year after surgery using POLYMAILLE® C
 
• Device failure during procedure or at discharge, at 30 days, 6 months and 1 year after surgery using POLYMAILLE® C
 

PROTOCOL	2020-PMC-01
TITLE:	Safety and Performance of POLYMAILLE® C vascular prosthesis
EFFECTIVE DATE:	15 January 2021

Safety secondary endpoints	
 
• Mortality rate during procedure or at discharge, at 6 months and 1 year after surgery using POLYMAILLE® C
 
• Limb salvage rate at 30 days, 6 months and 1 year after surgery using POLYMAILLE® C
 
• Adverse event during procedure or at discharge, at 30 days, 6 months and 1 year after surgery using POLYMAILLE® C
 

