Exploratory endpoints	
 
- After 1 year until the end of follow-up (5 years) using POLYMAILLE® C: 
 
○ Primary patency
 
○ Primary assisted patency
 
○ Secondary patency
 
○ Device failure
 
○ Mortality
 
○ Limb salvage
 
○ Adverse events
 
 
 
- Identify possible systematic misuse or off-label use of POLYMAILLE® C, with a view to verifying that the intended clinical purpose is correct.
 

Inclusion criteria	Subjects who did receive POLYMAILLE® C at least one year ago for replacement or bypass of pathological arteries.
Exclusion criteria	Patients who have objected to the collect of their data
Duration of the data collect:	6 months from first site operational to collect data until data delivery

---

PROTOCOL	2020-PMC-01
TITLE:	Safety and Performance of POLYMAILLE® C vascular prosthesis
EFFECTIVE DATE:	15 January 2021

---

---

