## 5. STUDY DESIGN

POLYMAILLE® C is a retrospective, observational, multicentre, descriptive study which examine short and long-term outcomes of using POLYMAILLE® C. This study will be done on all comers Real World Data to collect clinical safety and performance data on the device.

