### **5.3. Subjects**

The participating hospitals will screen all potential subjects and will select those who are appropriate for study inclusion, i.e. subjects implanted with POLYMAILLE® C for at least one year, or with complete data to death. As the study explores real world data, there is no exclusion criteria for subjects and all subjects with POLYMAILLE® C implanted for at least one year and up to 5 years will be included in the study.

All data will be retrieved from medical charts for each patient from time of surgery (considered as index date) until a maximum of 5 years after surgery.

Data from a minimum of 200 from 3 to 8 different sites in France will be evaluated. A minimum of 100 subjects will be evaluated for each main location of surgery (peripheral and abdominal).

Not more than 50% of study total enrolled subjects shall pertain to one unique centre.

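### Section 5.3.1 admits patients on the follow-up data they have, while the synopsis and section 5.3 admit them on time since implantation; the choice sets every denominator

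*Protocol*

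**What the plan says.** The protocol states who enters the study in several places, on two different bases.

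- **Time since implantation.** The synopsis inclusion row reads "Subjects who did receive POLYMAILLE® C at least one year ago for replacement or bypass of pathological arteries". The second sentence of section 5.3 says that "all subjects with POLYMAILLE® C implanted for at least one year and up to 5 years will be included in the study".
- **Available follow-up.** Section 5.3.1, worded as mandatory, requires: "Patient has a minimum of 1-year post-operative follow-up data available, or complete data to death".
- **In between.** The first sentence of section 5.3 selects "subjects implanted with POLYMAILLE® C for at least one year, or with complete data to death", which joins the time rule for some patients to the data rule for deaths. The synopsis Follow-up row, "At least 1 year follow-up after surgery until a maximum of 5 years", can be read as an entry condition or as an observation window.

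Section 5 describes the design in the words "This study will be done on all comers Real World Data". Section 8.1 puts every participating patient who met the eligibility criteria into the study population. Section 9.4 calculates endpoint proportions on non-missing observations. The two primary endpoints are primary patency at 1 year (section 7.1) and mortality at 30 days (section 7.2).

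**The concern.** The two bases admit different patients and nothing says which prevails. Eligibility defines the analysis population, so the choice fixes the denominator of both primary endpoints. Under section 5.3.1 the cohort is selected on information that arises after surgery, which is also when the endpoints occur.

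This cannot be repaired at analysis. Section 13 sends information letters only to patients who meet the inclusion criteria, so those screened out are never abstracted. Section 9.2 accepts that sites follow patients differently, and 3 to 8 sites could apply different rules in good faith.

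**Working it through.** **Step 1: the rules side by side.** Take three patients implanted 2 years before data extraction, reading time as time since surgery.

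| Patient | Synopsis inclusion row | 5.3, second sentence | 5.3.1 |
|---|---|---|---|
| A: alive and event-free when last seen at month 4 | in | in | out |
| B: graft occlusion documented at month 3, alive when last seen at month 4 | in | in | out |
| C: died within the first year, record incomplete | in | in | out |

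Patient A's 30-day status is known. So is patient B's, and B's 1-year result is known too: section 7.1 defines primary patency as a patent graft with no intervention on the conduit, so an occlusion at month 3 has already settled it. Section 5.3.1 removes both patients.

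**Step 2: 30-day mortality.** There is no figure in the plan to reproduce. The minimum of 200 (100 per location) rests on feasibility, and no event or loss rates are given. All rates below are assumptions.

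- m30 = true 30-day mortality; m1 = true 1-year mortality
- x = share of 1-year survivors without 1-year data
- y1 = share of 30-day deaths with incomplete records; y2 = the same share for deaths after day 30 and within 1 year

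Reported rate = m30(1−y1) / [m30(1−y1) + (m1−m30)(1−y2) + (1−m1)(1−x)]

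This exceeds m30 when 30-day deaths are retained more often than 30-day survivors, equals it when retention is the same, and falls below it only when 30-day deaths are retained less often. With m30 = 3% and m1 = 8%:

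| Assumption on deaths | x = 10% | x = 20% | x = 30% |
|---|---|---|---|
| All kept (y1 = y2 = 0) | 0.03/0.908 = 3.3% | 0.03/0.816 = 3.7% | 0.03/0.724 = 4.1% |
| 30-day deaths kept, half of later deaths lost (y1 = 0, y2 = 50%) | 0.03/0.883 = 3.4% | 0.03/0.791 = 3.8% | 0.03/0.699 = 4.3% |
| Half of all deaths lost (y1 = y2 = 50%) | 0.015/0.868 = 1.7% | 0.015/0.776 = 1.9% | 0.015/0.684 = 2.2% |

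If x, y1 and y2 are equal, the reported rate is 3.0%. In the first row at x = 30%, setting m1 to 5% gives 0.03/0.715 = 4.2%, and setting it to 15% gives 0.03/0.745 = 4.0%, so m1 matters little.

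For scale, 6 deaths in 200 (3%) has an exact 95% confidence interval of 1.1% to 6.4%. The shift of 0.3 points at x = 10% is small against that. The shift of 1.1 points at x = 30% is not negligible, and unlike sampling error it does not shrink with a larger sample.

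**Step 3: 1-year primary patency.** Two groups must be kept apart.

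- *Event-free patients without 1-year status (like A).* Their 1-year result is missing, so section 9.4 removes them from the proportion whichever entry rule is used. Their loss is not caused by section 5.3.1.
- *Living patients with a documented early failure, then lost (like B).* Their result is known, so section 9.4 would keep them. Section 5.3.1 alone removes them, which raises the reported proportion compared with one that counts them.

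The protocol gives nothing from which to size the second group.

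**The case against.** The best defence is that a minimum follow-up requirement is a recognisable choice for a retrospective, descriptive chart study whose stated gap (section 5.2) is mainly long-term evidence. Section 5.3.1 is the formal criterion and it keeps fully documented deaths. The Follow-up row and the first sentence of section 5.3 lean its way, so the synopsis could be read as shorthand. No hypothesis or acceptance threshold depends on the result.

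Part of this stands: the requirement is a possible design and the study is descriptive. But sections 5.3 and 5.3.1 are adjacent body text and disagree, so synopsis shorthand does not explain the conflict. Section 9.4 already provides for missing endpoints, so the data condition is not needed for that purpose.

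A reader might also infer more than the documents support:

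- **A survivor-only cohort.** Not so: the death clause keeps deaths with complete data.
- **Overstated and understated mortality as equally plausible.** Understatement needs incomplete records among the 30-day deaths themselves, more often than 30-day survivors are lost. Losing later deaths does not produce it, as the second row of the mortality table shows.
- **The whole loss of 1-year patency data as an effect of section 5.3.1.** Section 9.4 causes the event-free part under either rule.
- **The Study Population row as a promise to admit patients without follow-up.** The clause "but data will be collected for all subjects who did receive POLYMAILLE® C" follows a statement about surgical location and concerns location. The conflict does not rest on it, nor on the all-comers description in section 5, which is not an eligibility rule.

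**Conclusion.** The conflict in the text is certain and should be resolved before sites screen charts. Applying section 5.3.1 selects the cohort on post-operative information and discards known results. The harm is clearest for 30-day mortality and for documented early graft failures in living patients later lost.

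The size and net direction of any bias cannot be determined from the protocol. The figure of 3.3% to 4.1% against a true 3% assumes 1-year mortality of 8%, all deaths kept, and 10% to 30% of 1-year survivors dropped. It shows scale and predicts nothing about this study. No figure is offered for patency.

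**What to change.** 1. Use one criterion in the synopsis inclusion row and in sections 5.3 and 5.3.1: all patients, alive or dead, implanted at least 12 months before the site's data extraction, whatever follow-up is available, subject only to objection.
2. Reword the synopsis Follow-up row as the observation window. State whether the five-year limit in the second sentence of section 5.3 restricts the implantation date or only that window.
3. Estimate 30-day mortality in all patients with known 30-day status, and report how many are unknown.
4. Count documented early failures as failures in 1-year primary patency. In a simple proportion this pulls patency down if event-free patients without 1-year status are left out, so censoring the latter at their last assessment is the better partner. If that is done, amend the denominator rules in sections 8.1 and 9.4 to match, and note that censoring may be informative. Bias is then reduced, not removed.
5. Report per site the numbers implanted, objecting, and with known 30-day and 1-year status. Keep the subset meeting section 5.3.1 as a sensitivity analysis.

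The cost is wording changes in these sections, plus extra chart abstraction and information letters for patients with short follow-up, within the planned collection period ("6 months from first site operational to collect data until data delivery"). There will be more incomplete records. The minimum of 200 subjects, 100 per location, is unchanged.

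### The eligibility texts conflict on recent deaths: sections 5.3 and 5.3.1, applied literally, would admit deaths but no survivors from the last year of operations and bias mortality upward

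*Protocol*

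**What the plan says.** Four places in the protocol define who is eligible, in two different ways.

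**No surgery-date condition on the death branch**
- Section 5.3.1 has a single criterion: "Patient has a minimum of 1-year post-operative follow-up data available, or complete data to death".
- Section 5.3, first sentence, describes the appropriate subjects as "subjects implanted with POLYMAILLE® C for at least one year, or with complete data to death". Here death is an alternative to time since implantation itself.

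**Surgery at least a year ago, with no death branch**
- The synopsis, under study population: "Subjects who did receive POLYMAILLE® C at least one year ago for replacement or bypass of arteries".
- The synopsis, under inclusion criteria: "Subjects who did receive POLYMAILLE® C at least one year ago for replacement or bypass of pathological arteries".
- Section 5.3, second sentence, with an upper limit: "all subjects with POLYMAILLE® C implanted for at least one year and up to 5 years will be included in the study".

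The primary safety endpoint is "Mortality rate at 30 days after surgery using POLYMAILLE® C". Mortality at the procedure or discharge, at 6 months and at 1 year is secondary. Section 8.1 places every participating patient who meets the eligibility criteria in the study population. Section 9.4 computes endpoint proportions on non-missing observations, without imputation.

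**The concern.** Take two patients operated on the same day, four months before data extraction. One died on day 10 with a complete record. The other is alive. Under 5.3.1, and under the first sentence of 5.3, the first qualifies and the second cannot, because a year has not yet passed. The same holds for every operation in the last 12 months: its deaths can enter the numerator, but its survivors cannot enter the denominator. This is a calendar-time asymmetry and would persist even if every chart were complete.

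The rules in sections 8.1 and 9.4 do not correct it. A survival method could not repair it either, since the recent survivors would not be in the dataset. The study is justified in section 5.2 by insufficient evidence on safety and performance, so a selection effect on the primary safety endpoint matters. Sites that follow different eligibility texts would also apply different rules.

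**Working it through.** The protocol states no mortality rate and no derived sample size, so there is no figure of its own to reproduce. The check has two parts.

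**1. The example under each text** (operated 4 months before extraction)

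| Text | Died on day 10, complete record | Alive |
|---|---|---|
| Synopsis, population and inclusion | not eligible | not eligible |
| 5.3, second sentence | not covered | not covered |
| 5.3, first sentence | eligible | not eligible |
| 5.3.1 | eligible | not eligible |

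The first two rows treat the patients alike. The last two do not.

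**2. Size if 5.3 and 5.3.1 are applied literally**

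Assumed inputs:
- true mortality p = 3% at 30 days and q = 10% at 1 year;
- even accrual over W = 5 years before extraction, latest year included (suggested by the upper limit of 5 years in 5.3);
- cumulative mortality F(t) linear to p at h = 30/365.25 = 0.0821 years, then linear to q at 1 year;
- every death from the latest year is entered.

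Per unit of yearly accrual, for the latest year:
- all deaths seen before extraction = mean of F(t) = p·h/2 + (p+q)/2·(1−h) = 0.00123 + 0.05966 = 0.0609;
- deaths within 30 days = p·(1−h/2) = 0.03 × 0.9589 = 0.0288.

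Observed rates:
- enrolled = (W−1) + 0.0609 = 4.0609;
- 30-day mortality = (4 × 0.03 + 0.0288)/4.0609 = 0.1488/4.0609 = 3.66%, or 1.22 times the truth;
- 1-year mortality = (4 × 0.10 + 0.0609)/4.0609 = 0.4609/4.0609 = 11.35%, or 1.13 times the truth.

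Mortality at 6 months moves the same way. F(0.5) = 0.03 + 0.07 × (0.5 − 0.0821)/(1 − 0.0821) = 6.19%. The latest year contributes 0.0514 deaths within 6 months, the mean of min(F(t), F(0.5)). The observed rate is (4 × 0.0619 + 0.0514)/4.0609 = 7.36%.

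**Sensitivity** (same p and q)

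| Window including latest year | Share of recent deaths entered | 30-day | 1-year |
|---|---|---|---|
| 5 years | all | 3.7% | 11.35% |
| 5 years | half | 3.3% | 10.7% |
| 10 years | all | 3.3% | 10.6% |
| 3 years | all | 4.3% | 12.7% |
| 2 years | all | 5.5% | 15.2% |

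For the 5-year window with all recent deaths entered, assumed true 30-day mortality from 1% to 5% gives a relative excess of 21% to 23%.

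**In patients.** Of 200 enrolled, 200 × 4/4.0609 = 197 come from the eligible years and 3 are recent deaths. Expected 30-day deaths are 200 × 0.0366 = 7.3, against 6 at a true 3%. The exact 95% interval for 6/200 is 1.1% to 6.4%.

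**After the fix.** With one surgery-date condition for everyone, the latest-year terms vanish and the observed rates equal p and q.

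**The case against.** The strongest objection is that the one-year condition is in the protocol, and more than once: twice in the synopsis and again in the second sentence of 5.3, without an exception for deaths. A patient who dies in the first year cannot have a year of follow-up, so the natural purpose of the death clause in 5.3.1 is to replace follow-up length. Read together with the synopsis, 5.3.1 then produces no bias of this kind.

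Much of this stands. A reader might infer that the protocol has no surgery-date condition for patients who died, and that reported mortality will be inflated. The documents do not support that: the synopsis does impose the condition, and the inflation arises only if 5.3 and 5.3.1 are applied without it. What does not fall away is the conflict. The first sentence of 5.3 offers death as an alternative to time since implantation, not to follow-up length. Its second sentence says who will be included, not that others are excluded. Section 5.3.1 is the formal list, so a site that works from it would use the asymmetric rule.

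Three further limits also stand. The figures are an upper bound on assumed rates, and the 2- and 3-year windows have no basis in the documents. The effect does not depend on the window alone: the share of recent deaths entered matters, and the death rates matter slightly. Nor do the documents say that sites' windows differ, so loss of comparability between sites or locations is only a possibility. Finally, the study is descriptive, states no mortality threshold, and would err against the device; in the 5-year case the excess is about one death in 200, well inside sampling error. That limits the consequence but does not justify leaving a known bias in the primary safety endpoint.

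**Conclusion.** The point holds as a contradiction between eligibility texts with a conditional bias. The direction is certain if the literal reading of 5.3 and 5.3.1 is used: mortality at 30 days, 6 months and 1 year would be overstated. The size is not known, because the protocol gives neither the death rates nor a clear implant window. With true rates of 3% and 10%, even accrual, a 5-year window and all recent deaths entered, the upper bound is about 3.7% at 30 days and 11.35% at 1 year. It is smaller with a longer window or fewer recent deaths entered, and larger with a shorter window. Under the synopsis rule it is zero.

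A separate mechanism, the exclusion under 5.3.1 of survivors operated more than a year ago who lack one-year data, is not part of this point and is not removed by the fix below.

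**What to change.** Reconcile the synopsis (study population and inclusion criteria), section 5.3 and section 5.3.1. In 5.3 and 5.3.1, state one surgery-date window for every subject, alive or dead: index surgery with the device at least one year before the data-extraction date. Then state that, within this window, complete data to death replaces only the requirement for one year of follow-up and never the surgery-date condition. If the 5-year upper limit in 5.3 is meant to restrict the date of surgery, state it in the same sentence.

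The cost is one sentence of amendment. The downside is that a few recent deaths are left out of the analysis set. Section 11 provides only for vigilance reporting, so only those deaths that meet the vigilance criteria would be reported elsewhere.

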#### **5.3.2. Exclusion criteria**

Patients who have objected to the collect of their data.

---

PROTOCOL	2020-PMC-01
TITLE:	Safety and Performance of POLYMAILLE® C vascular prosthesis
EFFECTIVE DATE:	15 January 2021

---

## 6. RISKS AND BENEFITS OF THE DEVICE

### 6.1. Anticipated clinical benefits

There is no clinical benefit expected from the study as the evaluated device is already commercially available and used in routine, and as there will be no extra procedure for subjects who have been already implanted and followed. The study will only analyze already collected data.

There is no anticipated additional clinical benefit expected from the use of POLYMAILLE® C devices rather than other commercially available similar devices with same indications for use.

Anticipated clinical benefits of the device are thus equivalent to anticipated clinical benefits of open surgical vascular repair of abdominal and peripheral arteries.

Replacement or bypass of arteries presenting obliterative arterial disease (PAD) is required to restore the function of the artery: restore the blood flow to distal tissues. Anticipated clinical benefits may consist in patient's symptoms relief, improved quality of life and reduced tissular ischemia, amputation and mortality risks.

Replacement or bypass of arteries presenting aneurysmal disease is required to exclude the aneurysmal part without compromising the blood flow to distal tissues. Anticipated clinical benefits may consist in reduced risks of aneurysm associated thrombotic complications and reduced risk of aneurysm rupture and mortality.

### 6.2. Anticipated risks

There is no risk either associated to the study, as there is no procedure performed in the scope of the study. The risks listed below are those related to revascularization surgery and use of grafts and will be the ones monitored.

The type and rate of anticipated risks may differ according to indication and location of the surgical procedure, and may result in:

- Medically important event or reaction
- Persistent or significant incapacity or substantial disruption of the ability to conduct normal life functions
- Re-intervention and re-hospitalization or prolongation of existing hospitalization
- Life-threatening event, reaction up to death.

Early (peri-operative) and late adverse events of abdominal aortic and peripheral arteries open vascular repair with POLYMAILLE® C devices include:

- Bleeding
- Hematoma
- Adherence to surrounding tissues
- Allergic reaction

PROTOCOL	2020-PMC-01
TITLE:	Safety and Performance of POLYMAILLE® C vascular prosthesis
EFFECTIVE DATE:	15 January 2021

- Inflammatory reaction / oedema
- Seroma / lymphorrhea formation
- Wound complications: infection (superficial or deep), revision
- Graft infection
- Graft dilatation
- Pseudo aneurysm / false aneurysm (para-anastomotic aneurysm; non-anastomotic aneurysm)
- Graft stenosis / occlusion
- Limb occlusion
- Amputation (major or minor)
- Secondary aorto-enteric fistula
- Renal dysfunction
- Neurologic deficit
- Pericardial effusion
- Pulmonary complication (pneumonia, perioperative acute pulmonary oedema)
- Cardiac complications (myocardial infarction or arrhythmia, ischemic heart disease, atrial fibrillation)

